5.2 ASSESSMENT OF EFFICACY

Response and progression will be evaluated in this study using Response Evaluation Criteria in Solid Tumors (RECIST) guideline (version 1.1) (9). Tumor response will be assessed by investigator.

See APPENDIX 10.4, RECIST 1.1 Criteria for details on lesion measurements and response assessment.

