10.4 APPENDIX 4 RECIST 1.1 CRITERIA

The criteria below are based on RECIST 1.1 (9).

The preferred method of assessment is a spiral CT scan with IV and oral contrast, unless IV and/or oral contrast are medically contraindicated. CT scans of the chest, abdomen and other areas of known or newly suspected disease must be performed. Scans of the abdomen, pelvis and other areas of the body, but not chest, may be done with MRI instead of CT.

Skin lesions followed as target lesions must be documented by color digital photography and must include in the image a ruler with millimeter subdivisions and a label that includes the patients ID and date.

Bone scans (using ^{99}m -technetium polyphosphonate scintigraphy) are recommended at baseline if the patient has any signs and symptoms consistent with bone metastasis or a history of bone metastasis. Bone metastasis identified at baseline must be documented and assessed according to RECIST 1.1 at the times of the other tumor measurements indicated in the flow chart. During the study bone scans should be repeated as clinically indicated in patients without bone metastasis at Baseline.

For the purposes of this study, patients should be re-evaluated for response at weeks 8, 16 and every 8 weeks thereafter. In the event of a treatment delay, interruption or discontinuation of treatment, tumor assessment should continue to follow the original schedule.

Follow-up tumor assessments must utilize the same CT/MRI/photographic method and acquisition technique (including use or non-use of IV contrast) as were used for screening assessments to ensure comparability. A chest x-ray or skeletal x-ray which clearly demonstrates a new metastatic lesion may be used to document progression in lieu of CT/MRI/bone scan.

Only those patients who have measurable disease present at baseline, have received at least 3 weeks of therapy, and have had their disease re-evaluated will be considered evaluable for response. These patients will have their response classified according to the definitions stated below.

Measurability of tumour at baseline**Measurable lesions**

Lesions that can be accurately measured in at least one dimension with longest diameter ≥ 10 mm (by CT scan, MRI, caliper measurement) or ≥ 20 mm (by chest X-ray). Pathological lymph nodes, defined as lymph nodes with a short axis >15 mm are also measurable.

Measurable disease

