Measurable disease requires the presence of at least one measurable lesion. Measurable lesion if limited to either small (<2cm) solitary visceral lesion or scant (<5cm) lymph nodes only metastasis should be evaluated for additional evidence of malignant nature and discussed with the sponsor before enrolling.

Non-measurable disease

Non-measurable lesions are all other lesions, including small lesions (longest diameter <10 mm with CT scan, MRI or caliper measurement or <20 mm with chest X-ray or pathological lymph nodes with shortest axis \geq 10 and <15 mm) as well as truly non-measurable lesions. Lesions considered truly unmeasurable include leptomeningeal disease, ascites, pleural or pericardial effusion, inflammatory breast disease, lymphangitic involvement of skin or lung, abdominal masses/ abdominal organomegaly identified by physical exam that is not measurable by reproducible imaging techniques.

New lesions in irradiated fields

Previously irradiated lesions should not be used as indicator lesions. However, new lesions occurring in previously irradiated fields can be used to assess the antitumor response.

Methods of measurement

All measurements must be recorded in metric notation, using a ruler or callipers. All baseline evaluations must be performed as close as possible to the treatment start and never more than 4 weeks before the beginning of the treatment. If a lesion is considered too small to measure, a default measurement of 5mm should be applied. If the lesion is not visible, a default measurement of 0mm should be applied.

The same method of assessment and the same technique must be used to characterise each identified and reported lesion at baseline and during follow-up.

Clinical lesions will only be considered measurable when they are superficial (e.g., skin nodules, palpable lymph nodes). In the case of skin lesions, documentation by colour photography including a ruler to estimate the size of the lesion is obligatory.

CT and MRI are the best currently available and reproducible methods to measure target lesions selected for response assessment. Conventional CT and MRI should be performed with cuts of 5 mm or less in slice thickness contiguously. Spiral CT should be performed using a 5 mm contiguous reconstruction algorithm. This applies to the chest, abdomen and pelvis.

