Ultrasound, endoscopy and laparoscopy should not be used to measure tumour lesions or evaluate tumour response. However, these techniques can be useful to supplement information from other techniques.

Cytology and histology can be used to differentiate between PR and CR in rare cases (for example, residual lesions in tumour types such as germ cell tumours where known residual benign tumours can remain).

Baseline Documentation of Target and Non-target Lesions

All measurable lesions up to a maximum of two lesions per organ and five lesions in total, representative of all involved organs should be identified as target lesions and will be recorded, measured (longest diameter = LD) and numbered at baseline. Target lesions should be selected on the basis of their size (lesions with the longest diameter) and their suitability for accurate repetitive measurements (either by imaging techniques or clinically). Lymph nodes must be $\geq 15\text{mm}$ in order to be considered as target lesions.

A sum of the longest diameter (LD) for all target lesions will be calculated and reported as the baseline sum LD. The baseline sum LD will be used as reference to further characterise the objective tumour response of the measurable dimension of the disease (see Table 10.4:1).

Table 10.4: 1 Evaluation of target lesions

Complete Response (CR)	Disappearance of all target lesions.
Partial Response (PR)	At least a 30% decrease in the sum of LD of target lesions taking as reference the baseline sum LD.
Progression (PD)	At least a 20% increase in the sum of LD of target lesions taking as reference the smallest sum LD recorded since the treatment started, together with an absolute increase in the sum of LD of at least 5mm. OR The appearance of one or more new lesions.
Stable Disease (SD)	Neither sufficient shrinkage to qualify for PR, taking as reference the baseline SoD, nor sufficient increase to qualify for PD taking as reference the smallest SoD since the treatment started.

All other lesions (or sites of disease) should be identified as non-target lesions and should also be recorded at baseline. Measurements are not required and these lesions should be followed as "present" or "absent" (see Table 10.4:2).

Table 10.4: 2

Evaluation of non-target lesions and new lesions

Complete Response (CR)	Disappearance of all non-target lesions and normalisation of tumour marker level. All lymph nodes must be non-pathological in size (<10 mm short axis)

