Non-CR/Non-PD	Persistence of one or more non-target lesions or/and maintenance of tumour marker level above normal limits.
Progression (PD)	Appearance of one or more new lesions and/or unequivocal progression of existing non-target lesions. Although a clear progression of non-target lesions only is exceptional, in such circumstances, the opinion of the treating physician should prevail and the progression status should be confirmed later by the review panel (or study chair).

In some circumstances it may be difficult to distinguish residual disease from normal tissue. When the evaluation of complete response depends upon this determination, it is recommended that the residual lesion be investigated (fine needle aspirate/biopsy) before confirming the complete response status.

Confirmation

In case of tumour response (CR or PR), confirmation will be performed with a repeat assessment no less than 4 weeks after the RECIST criteria for response have been met. In the case of SD, measurement must have met the SD criteria at least once after study entry at an interval of not less than 6 weeks.

Evaluation of best response to study treatment

The best response to study treatment (Table 10.4: 3) is the best response recorded from the start of treatment until disease progression or start of further anti-cancer treatment (taking as reference for progressive disease the smallest measurements recorded since the treatment started). In general, the patient's best response assignment will depend on the achievement of both measurements and confirmation criteria (Table 10.4: 3).

Patients with a global deterioration of health status requiring discontinuation of treatment without objective evidence of disease progression at that time should be reported as "symptomatic deterioration". Every effort should be made to document the objective progression even after discontinuation of treatment.

Table 10.4: 3 Algorithm for evaluation of overall response

Target lesions	Non-target lesions	New lesions	Overall response
CR	CR	No	CR
CR	Non-CR/ Non-PD	No	PR
CR	Not evaluated	No	PR
PR	Non-PD or not evaluated	No	PR
SD	Non-PD or not evaluated	No	SD
Not evaluated	Non-PD	No	NE
PD	Any	Yes or No	PD
Any	PD	Yes or No	PD
Any	Any	Yes	PD

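### As worded, Appendix 10.4 leaves the baseline sum out of the progression reference, so progression can be called late in target lesions that grow from the outset

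*Combined protocol and SAP*

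**What the plan says.** Section 5.2 has the investigator assess response and progression by RECIST 1.1 and sends the reader to Appendix 10.4 for the details. The appendix says it is based on RECIST 1.1 and that evaluable patients are classified by the definitions it sets out.

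Table 10.4:1 uses two reference values for target lesions:

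- **Partial response:** a fall of at least 30% from the baseline sum of longest diameters.
- **Progression:** a rise of at least 20%, "taking as reference the smallest sum LD recorded since the treatment started". The rise must also reach 5 mm in absolute terms. A new lesion counts as progression on its own.
- **Stable disease:** too little shrinkage from baseline for a partial response, "nor sufficient increase to qualify for PD taking as reference the smallest SoD since the treatment started".

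The paragraph on best response repeats the on-treatment reference: "taking as reference for progressive disease the smallest measurements recorded since the treatment started".

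On timing, the appendix requires baseline evaluations close to the start of treatment and "never more than 4 weeks before the beginning of the treatment". The flow chart likewise places screening scans within the 28 days before treatment. After that, "patients should be re-evaluated for response at weeks 8, 16 and every 8 weeks thereafter".

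The paragraph directly above the table is more general: "The baseline sum LD will be used as reference to further characterise the objective tumour response of the measurable dimension of the disease".

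**The concern.** A sum measured before treatment is not one recorded since treatment started. The table calls baseline by name where it means baseline, and the stable-disease row sets the two references side by side in one sentence. Read as written, baseline is therefore not part of the reference for growth.

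This matters only when baseline is the smallest sum the patient ever has, that is, when the target lesions never shrink below it. Such tumours are the ones most likely to progress early. At the first scan the rule gives them no earlier on-treatment sum. At later scans it measures growth from a sum that is already enlarged.

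Progression is the event for progression-free survival, for which Section 7.3 plans a Kaplan-Meier median, and it closes the window for best response. A deferred call moves a patient's event to a later scan, at least 8 weeks on unless another route to progression intervenes, and can turn a progression into stable disease. Assessment is by the investigator. The one later confirmation that the appendix describes concerns progression of non-target lesions, so no stated step would catch the difference.

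**Working it through.** The plan gives no figure that depends on this definition, so there is nothing to reproduce. The check applies the rule in Table 10.4:1 under two readings.

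**Inputs.** From Table 10.4:1: relative threshold 20%, absolute threshold 5 mm. From Appendix 10.4: scans at baseline (before treatment), week 8 and week 16. The lesion sums in mm are assumed for illustration.

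**Rule.** With reference R and current sum S, progression requires S/R ≥ 1.20 and S − R ≥ 5 mm.

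- Reading A (as worded): R is the smallest on-treatment sum.
- Reading B (baseline included): R is the smallest sum on study, counting baseline.

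**Step 1: week 8.** Under A the only on-treatment sum is the week-8 sum itself, so the rise is 0% for every patient. Going from 50 to 65 mm gives 65/65 − 1 = 0% under A, and 65/50 − 1 = +30% with +15 mm (progression) under B. The rule under A is empty at this scan.

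**Step 2: week 16, where both readings can be applied.** Take 50 mm at baseline, 58 mm at week 8, 66 mm at week 16.

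| Scan | Sum | Reading A | Reading B |
|---|---|---|---|
| Week 8 | 58 | no earlier on-treatment sum | 58/50 − 1 = +16%: not progression |
| Week 16 | 66 | 66/58 − 1 = +13.8%, +8 mm: stable | 66/50 − 1 = +32%, +16 mm: progression |

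Week 8 is not progression on either reading, so the week-16 disagreement does not depend on how the empty first scan is handled. The 5 mm condition is met both ways at week 16; the relative condition separates the readings.

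**Step 3: how wide the gap is.** In this case B calls progression from 1.20 × 50 = 60 mm and A from 1.20 × 58 = 69.6 mm. Any later sum from 60 mm to just under 69.6 mm is progression under B and stable under A. The upper end is 69.6/50 − 1 = 39.2% above baseline. In general, if the week-8 sum lies between baseline and 20% above it, the threshold under A can rise to just under 1.20 × 1.20 = 1.44 times baseline.

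**Step 4: where the readings agree.** If the tumour first shrinks, say from 50 to 40 mm, the reference is 40 mm under both, and both call progression at 1.20 × 40 = 48 mm (+8 mm). The wording has no effect there.

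**The case against.** The case against is substantial.

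- **The text nowhere says that baseline is excluded.** The sentence above the table makes the baseline sum a reference for characterising response and points to the whole table. This is fair, but the progression row then states its own, different reference, and a specific row prevails over a general introduction.
- **The literal reading defeats itself at week 8.** An increase needs an earlier value. Stable disease must be met at an interval of at least 6 weeks from study entry, so the week-8 scan is meant to separate stable from progressive disease. Follow-up scans must also match the screening technique so that they can be compared. Most assessors would fall back on baseline at that scan. This stands. A reader might infer that week-8 target growth can never be scored as progression; the documents do not support that as a description of practice. The fallback does not settle week 16, where the worded rule can be applied and gives a different answer.
- **RECIST 1.1 governs.** Section 5.2 says so and no departure is announced. This supports reading baseline in, but the standard's text is not in the documents, and Section 5.2 refers the reader to this appendix for the detail.
- **Other routes to progression remain.** New lesions and unequivocal non-target progression count without any reference sum, and Section 6.2.3.3.1 accepts clinical progression as an end to follow-up for progression. This stands and narrows the group affected.
- **Treatment is not tied to the table.** Sections 3.1 and 6.2.2 stop treatment for unequivocal progression on examination or imaging, not for a percentage in Table 10.4:1. It would be tempting to infer that misclassified patients must stay on treatment; the documents do not say that.
- **The primary endpoint's basis is intact.** Partial response is measured from baseline, and Section 7.2 sizes the trial on response rate. This stands.

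**Conclusion.** The point holds as a defect in a stated definition. Followed as written, the progression and stable-disease rows and the best-response paragraph omit baseline from the growth reference. In tumours that grow from the outset, this can turn a progression into stable disease and date the event later. The 50/58/66 mm case shows opposite calls at week 16 from the same measurements.

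The size for the trial cannot be given. It depends on how many patients progress by target growth alone without first shrinking, and on how many assessors already count baseline; the documents report neither. A reader might infer that progression-free survival is overstated. What the documents support is that it can be, if the wording is applied literally. Nor can a cohort effect be read from early progression rates or from one patient's 8-week delay: early events include deaths, new lesions and non-target progression, which are unaffected, and one patient's delay is not a shift in the median.

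The consequence is confined to the secondary endpoint of progression-free survival and to the stable-disease rate. The partial-response threshold and the sample size are unchanged. The lesion sums in the worked cases are assumed; the thresholds and scan times are the plan's.

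**What to change.** In the progression and stable-disease rows of Table 10.4:1, and in the best-response paragraph of Appendix 10.4, define the reference for growth as *the smallest sum recorded on study, including the baseline sum if that is the smallest*. Then check existing stable-disease calls and progression dates at every scan, not only the first, against this definition using the recorded lesion measurements. The check does not presume that any call was wrong; it establishes whether any was.

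The cost is a one-line change in three places and a small recalculation from data already held. No new scans are needed. Progression-free survival may come out slightly less favourable.
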